1.1.2 Secondary Objectives

1.1.2.1 To examine baseline to 8-week changes in disease-specific quality of life, pain severity, pain-related anxiety, depression, and heart rate variability in patients receiving the ACT intervention.

1.1.2.2 To examine between-group differences in disease-specific quality of life, pain severity, pain-related anxiety, depression, and heart rate variability from baseline to 8 weeks.

1.1.2.3 To examine patterns of change from baseline to 8 weeks to 32 weeks in all primary and secondary outcome measures.

1.1.2.4 To examine potential mediators between pre- and post-treatment pain interference, including pain acceptance, psychological flexibility, as well as cognitive diagnosis (ADHD, LD), disease characteristics (stable vs. progressive disease, location of plexiform neurofibroma), and recent life events to determine whether these variables influence the effectiveness of the intervention.

1.1.2.5 To compare the reliability and validity of the two pain interference measures: the Pain Interference Index (PII) and the PROMIS Pain Interference scale.

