1.2.4 General Overview

The proposed study will use a randomized controlled trial design to compare the treatment group (Acceptance and Commitment Training; ACT) to a wait-list group (WL) in adolescents and young adults ages 16 – 59 years with NF1 and PNs who report chronic pain. Patients will be recruited from [name] NF1 program at the National Cancer Institute, from NF1 clinics around the country, and via the Children's Tumor Foundation (CTF) registry. With all patients, we will implement an 8-week in-person and internet-delivered ACT intervention. All participants will complete their Time 1 assessment (ECG and questionnaires) on day 1 at the NIH before being randomized.

Participants assigned to the ACT group will meet with a trained ACT therapist for two in-person sessions at the NIH (days 1 and 2). Upon returning home, weekly emails will be sent to patients

for 8 weeks, each containing ACT-related information and exercises to complete at home. Video chat sessions will be conducted via computer at weeks 2, 4, and 6. These patients will return to the NIH at week 8 for their Time 2 assessment (repeat ECG and questionnaires). They will be encouraged to continue using ACT techniques in their daily lives. They will be sent follow-up questionnaires to complete electronically from home six months following completion of the 8-week intervention (week 32; Time 3).

Participants assigned to the WL group will return home after completing the Time 1 baseline assessment. They will return to the NIH at week 8 to complete Time 2 follow-up measures (ECG, questionnaires); these data will serve as the primary comparison with the ACT group and will also serve as their baseline assessment for the ACT arm. These participants will then receive the same ACT intervention as described above (two 2-hour in-person sessions, weekly emails, biweekly video chat sessions). They will return to the NIH after the 8-week ACT intervention (at about week 16) to repeat follow-up measures, and will then be encouraged to continue using ACT techniques in their daily lives. Six months later (week 40), they will complete questionnaires online from home. Thus, because they cross over to the ACT intervention after the wait-list period, participants in this group will complete the measures a total of 4 times (as opposed to 3 times in the ACT immediate intervention group).

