2.3.1.4 Randomization and Arm Assignment

All patients in cohort 1 will be stratified for age and randomized between arms 1 and 2. After patients have been on the Wait List Arm for 8 weeks, they will cross over to the ACT arm.

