6 STATISTICAL SECTION

6.1 PRIMARY AND SECONDARY OUTCOMES

The primary objective of the trial is to compare pain interference mean score changes from baseline to 8 weeks between the ACT intervention group and the WL group. In the pilot study conducted by our group, mean scores on PII self-report went from 2.1 (1.0) to 1.5 (1.1), with paired differences having a mean change of -0.68 and SD=1.3. Based on this preliminary estimated change for the ACT group, and an assumption of no change in the WL group and a corresponding, reduced SD = 0.8, forty-one patients will be needed per group to have 80% power to detect a difference in change score between the two arms of -0.68, using a t-test with significance level of .05 (two-sided). Secondary analyses will be performed to compare between-group changes from baseline to 8 weeks and from baseline to 32 weeks on the following endpoints: disease-related quality of life, pain severity, pain-related anxiety, and depression. Given the wide age range of the study, we will stratify analyses by age (16 – 24 years; 25 – 59 years). Descriptive statistics will be computed on the primary and secondary outcome measures (means, standard deviations, etc.). If there are significant differences between the groups at baseline (for example, with respect to gender or number of patients on pain medication), analysis of covariance (ANCOVA) may be used to control for these differences statistically during follow-up analyses (treating baseline as a covariate). We also will assess for differences between the group randomized to ACT and the WL group on primary and secondary outcomes, particularly comparing primary results from 0 to 8 weeks for ACT vs. 8 to 16 weeks for WL (receiving ACT starting at 8 weeks); if the results are similar (for example, $p>0.30$ approximately), we will combine these groups to report the overall effect of ACT for 8 weeks, and also examine changes from baseline to 8 weeks and 8 to 16 weeks using an appropriate statistical test. Finally, based on a priori hypotheses and prior literature, we will test for indirect effects of acceptance and psychological flexibility with simple mediation model analyses. We will generate 5,000 bootstrapped samples using Preacher and Hayes' (Preacher & Hayes, 2004) INDIRECT macro. Post-treatment scores will be used for these analyses. Additionally, we will examine whether a previous cognitive diagnosis (ADHD or learning disability), reading ability, disease characteristics (stable vs. progressive disease, location of plexiform neurofibroma), or recent life events, relate to changes over time in the primary outcome with an ANOVA, and if so

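### Section 6.1 plans a 32-week between-group comparison with no untreated wait-list data behind it, and pools two ACT periods on a non-significant test (p > 0.30)

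*Combined protocol and SAP*

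**What the plan says.** Section 6.1 plans secondary analyses "to compare between-group changes from baseline to 8 weeks and from baseline to 32 weeks on the following endpoints": quality of life, pain severity, pain-related anxiety and depression. The objectives are narrower. Objective 1.1.2.2 reads "To examine between-group differences in disease-specific quality of life, pain severity, pain-related anxiety, depression, and heart rate variability from baseline to 8 weeks". Objective 1.1.2.3 asks for "patterns of change from baseline to 8 weeks to 32 weeks in all primary and secondary outcome measures" and does not ask for a contrast between arms.

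For the wait-list (WL) arm, Section 2.3.1.4 states: "After patients have been on the Wait List Arm for 8 weeks, they will cross over to the ACT arm". Section 1.2.4 continues: "They will return to the NIH after the 8-week ACT intervention (at about week 16) to repeat follow-up measures", and then "Six months later (week 40), they will complete questionnaires online from home". The same section says that the WL week-8 data "will also serve as their baseline assessment for the ACT arm".

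Section 6.1 also compares the ACT arm's change over weeks 0–8 with the WL arm's change over weeks 8–16, when WL patients are receiving ACT. If the results are similar, with p above about 0.30 given as an example, "we will combine these groups to report the overall effect of ACT for 8 weeks". No margin or confidence-interval criterion is given. The sentence ends by adding that the changes over the two periods will also be examined with a suitable test.

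**The concern.** **The 32-week contrast.** Section 6.1 does not say what 32 weeks means for the WL arm. If it means calendar week 32, the study has no WL questionnaires at that point. If it means 32 weeks after each arm's own pre-ACT baseline, data exist in both arms, but every WL patient has by plan crossed over to ACT. The result could then be read as a longer-term ACT-versus-control finding, which it is not.

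**The pooling rule.** A p-value above 0.30 does not show that two changes agree. It shows only that this sample did not separate them. The pooled number is a pre-post change with no concurrent control, so regression to the mean, natural course and expectation all remain in it. Calling it the overall effect of ACT places it beside the randomised estimate as if the two had the same standing. Assessment conditions can also differ: Section 3.1.2 brings all patients to the NIH at week 8 but lets WL patients answer week 16 from home in cases of hardship.

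**Working it through.** **1. The plan's own figure.** Section 6.1 gives a difference in change of −0.68, SDs of 1.3 (ACT) and 0.8 (WL), two-sided 0.05 and 80% power. The root-mean-square SD is √((1.3² + 0.8²)/2) = 1.079. The noncentral t gives power 0.795 at 40 per group and 0.805 at 41, so the stated 41 per group reproduces. Nothing below changes it.

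**2. Assessments by arm** (schema in Section 1.2.4, calendar in Section 3.4, ECG text in Section 3.3.2):

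| | ACT | WL |
|---|---|---|
| Questionnaires, weeks | 0, 8, 32 | 0, 8, 16, 40 |
| ECG, weeks | 0, 8 | 0, 8, 16 |
| ACT begins | week 0 | week 8 |

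- Calendar reading: WL questionnaires scheduled at week 32: none.
- Aligned reading: week 40 − week 8 = 32 weeks, so WL data exist. WL patients still untreated by plan after week 8: none.
- Baseline to 8 weeks in the same sentence must use WL week 0 to be the randomised comparison. On the aligned reading, one sentence would therefore use two different WL baselines.
- Neither arm has an ECG at the six-month follow-up, so heart rate variability cannot contribute to objective 1.1.2.3 at that time.

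**3. Operating characteristics of the p > 0.30 rule.** Inputs are 41 per group, 80 degrees of freedom and a two-sided t-test. The documents give no SD for WL change during weeks 8–16, so three pairs are assumed. The differences tried are 0, 0.34 (illustrative, half the design effect) and 0.68 (the design effect).

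- SE = √(s₁²/41 + s₂²/41)
- Largest observed difference that is pooled = t(0.85) × SE
- 95% CI half-width = t(0.975) × SE
- Probability of pooling = probability that |t| is below t(0.85), from the noncentral t with noncentrality difference/SE

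| Assumed SDs (ACT 0–8 / WL 8–16) | 1.3/1.3 | 1.3/0.8 | 0.8/0.8 |
|---|---|---|---|
| SE | 0.287 | 0.238 | 0.177 |
| Largest difference pooled | 0.30 | 0.25 | 0.18 |
| 95% CI half-width | 0.57 | 0.47 | 0.35 |
| Upper 95% limit at p = 0.30 | 0.87 | 0.72 | 0.54 |
| Pools if true difference is 0 | 70% | 70% | 70% |
| Pools if true difference is 0.34 | 43% | 34% | 19% |
| Pools if true difference is 0.68 | 9% | 4% | 0.3% |

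Simulated t-tests (200,000 runs) at 0.34 gave 43.0%, 34.3% and 18.8%.

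**4. When a pooled result still leaves 0.68 open.** The 95% CI includes 0.68 once the observed difference exceeds 0.68 minus the half-width:

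- 1.3/1.3: 0.68 − 0.57 = 0.11, p = 0.71. Affected pooled results: p from 0.30 to 0.71.
- 1.3/0.8: 0.68 − 0.47 = 0.21, p = 0.39. Affected pooled results: p from 0.30 to 0.39.
- 0.8/0.8: 0.68 − 0.35 = 0.33, p = 0.07. The rule would not pool there, so none are affected.

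**The case against.** **On 32 weeks.** The aligned comparison is feasible with planned data, and immediate versus delayed ACT is a legitimate question if labelled so. Section 6.1 never calls it ACT versus control, and the 8-week data are the stated primary endpoint. It follows that the analysis need not fail. But Section 6.1 names neither the WL baseline nor the WL follow-up week, and no objective asks for a between-group difference beyond 8 weeks.

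**On pooling.** Several points are fair:

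- The threshold is an example, is stricter than 0.05, and governs only a secondary estimate. A true difference of 0.68 would rarely pass it.
- Declining to pool identical periods 30% of the time costs only a summary figure.
- Section 6.1 ties SD 0.8 to untreated WL patients. Both periods here are ACT periods, so 1.3/1.3 is closest to the SD given for ACT; the other two pairs serve as a range.
- Objective 1.1.2.1 asks for within-group change under ACT, so a pre-post figure has a place.
- Examining the two periods is already planned.
- Section 4.1 has all questionnaires completed by computer or tablet, so answering from home changes the setting but not the mode. Little rests on this point.

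These limit the seriousness but do not remove the defect. The planned examination of both periods gives no confidence interval for their difference and leaves the gate in place. Objective 1.1.2.1 is served equally well by a pre-post change labelled uncontrolled.

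**On heart rate variability.** The 32-week endpoint list in Section 6.1 already omits it. The mismatch is in objective 1.1.2.3, which covers all outcomes.

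**Conclusion.** Both parts hold, and both should be fixed. The 32-week between-group comparison has no WL data on the calendar reading and no untreated comparator on either reading. This follows from the schedule and needs no assumption.

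The pooling rule treats non-significance as similarity. With 41 per group it would combine periods that differ by 0.34 points between 19% and 43% of the time, depending on the assumed SDs. Under two of the three SD pairs, a result that qualifies for pooling can still be compatible with a difference as large as the 0.68 design effect. Under 0.8/0.8 it cannot. These figures rest on the assumed SDs, the illustrative 0.34 and full data on 41 per group. That the pooled figure is uncontrolled does not depend on them.

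The primary comparison, the other randomised 8-week comparisons, alpha and the sample size are not affected.

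**What to change.** 1. In Section 6.1, delete the extension of the between-group analyses to 32 weeks. Replace it with within-arm change aligned on the start of ACT, from pre-ACT baseline through end of ACT to six-month follow-up (ACT weeks 0, 8, 32; WL weeks 8, 16, 40), labelled uncontrolled.
2. Limit objective 1.1.2.3 to questionnaire outcomes.
3. Drop the p > 0.30 gate. Always report the ACT 0–8 and WL 8–16 changes separately, with a 95% CI for their difference. Label any pooled pre-post change descriptive and uncontrolled, and keep the term effect of ACT for the randomised 0–8 week comparison.

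A formal equivalence test is not a realistic substitute. With SD 1.3 and an assumed margin of 0.34, 80% power needs 2 × (1.3 × (1.645 + 1.282)/0.34)², about 251 per group.

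The cost is wording in Section 6.1 and objective 1.1.2.3. There are no new visits or data, and no change to sample size, alpha or the primary analysis. No between-group objective is lost, because 1.1.2.2 stops at 8 weeks. What is given up is a headline pooled effect.

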
we may control for these variables in other analyses with an ANCOVA. Finally, we will compare the psychometric properties of the PII and PROMIS Pain Interference Scale by examining internal consistency in the patient sample (computed by Pearson correlations) and the response to change (as described in the primary objective analysis above). Data will be entered into a secure database, then analyzed using SAS statistical software.

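### Section 6.1 leaves baseline PII out of the primary comparison unless a baseline difference happens to be significant, and does not say how age stratification enters the analysis

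*Combined protocol and SAP*

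**What the plan says.** Section 6.1 defines the primary comparison as mean PII change from baseline to 8 weeks, ACT against WL. It gives no separate statement of the analysis model. The only test attached to this comparison is in the sample-size sentence: "using a t-test with significance level of .05 (two-sided".

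ANCOVA appears twice in 6.1, both times as an option:

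- The first is conditional: "If there are significant differences between the groups at baseline", with gender and pain medication as examples, then "analysis of covariance (ANCOVA) may be used to control for these differences statistically during follow-up analyses (treating baseline as a covariate".
- The second concerns cognitive diagnosis, reading ability, disease characteristics and life events: "we may control for these variables in other analyses with an ANCOVA".

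On age, the text says "we will stratify analyses by age (16 – 24 years; 25 – 59 years". These bands match the randomisation strata in section 2.3.1.3. Whether this means a model term, a stratified test or separate analyses is not stated, nor whether it covers the primary test.

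Secondary endpoints are to be analysed to "compare between-group changes from baseline to 8 weeks and from baseline to 32 weeks". Section 2.3.1.4 has the control arm leave its control condition at week 8: "After patients have been on the Wait List Arm for 8 weeks, they will cross over to the ACT arm". Section 1.2.4 places that arm's last questionnaires later than week 32: "Six months later (week 40), they will complete questionnaires online from home".

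**The concern.** Every participant provides a baseline PII score, and it is likely to predict the week-8 score. A change-score t-test implicitly fixes the slope on baseline at 1. ANCOVA estimates the slope, so apart from one degree of freedom it can only equal or improve precision.

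The conditional rule does not replace this. A test of baseline balance after randomisation is significant about 5% of the time by chance, whether or not the variable matters for outcome. The trigger, the covariate list and the scope (does the phrase about follow-up analyses include the primary test?) are all open. It is also unclear whether the baseline named as covariate is baseline PII or the imbalanced characteristic. More than one primary result would therefore be consistent with the text.

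**Working it through.** **Inputs from section 6.1.** Difference in change 0.68 PII points; change SD 1.3 (ACT) and 0.8 (WL); pilot SDs 1.0 at baseline and 1.1 at follow-up; 41 per arm; two-sided 0.05. **Assumption, not in the documents:** WL SD of 1.0 at both visits.

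**The plan's own figure.** Average change variance = (1.3² + 0.8²)/2 = (1.69 + 0.64)/2 = 1.165. Noncentral-t power is 80.5% at 41 per arm and 79.5% at 40. The stated 41 is reproduced.

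**Covariances implied by the change SDs**, from (SD₀² + SD₈² − SD_change²)/2:

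- ACT: (1.00 + 1.21 − 1.69)/2 = 0.26; correlation 0.26/(1.0 × 1.1) = 0.24.
- WL: (1.00 + 1.00 − 0.64)/2 = 0.68; correlation 0.68.

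**ANCOVA with a common slope.** Slope = (0.26 + 0.68)/(2 × 1.00) = 0.47. Residual variances:

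- ACT: 1.21 − 2 × 0.47 × 0.26 + 0.47² = 1.187.
- WL: 1.00 − 2 × 0.47 × 0.68 + 0.47² = 0.582.
- Average: 0.884, against 1.165 for change scores.

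| | t-test on change | ANCOVA |
|---|---|---|
| Standard error | √(2 × 1.165/41) = 0.238 | √(2 × 0.884/41) = 0.208 |
| 95% CI half-width (× 1.99) | 0.47 | 0.41 |
| Power at 41 per arm | 80.5% | 89.9% |
| n per arm for 80% power | 41 | 32 |

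The standard error falls by 1 − 0.208/0.238 = 13%.

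**Sensitivity.** Change SDs are held at 1.3 and 0.8 while the visit SDs vary:

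| Baseline SD | ACT week-8 SD | WL week-8 SD | ANCOVA power |
|---|---|---|---|
| 0.7 | 1.4 | 1.2 | 80.5% |
| 0.8 | 1.1 | 1.0 | 86.9% |
| 1.0 | 1.1 | 1.2 | 86.4% |
| 1.0 | 1.1 | 0.8 | 93.1% |
| 1.2 | 1.1 | 0.8 | 95.9% |

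Over a grid of 120 cases (baseline 0.7–1.2, ACT week-8 1.1–1.4, WL week-8 0.8–1.2, steps of 0.1) the gain runs from 0.0 to +15.5 points, with quartiles +3.0, +6.0 and +9.1. The cells are equally weighted, so this is a range, not a distribution.

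**The conditional rule.** The simulations used 20,000 trials per case, and their ANCOVA also carries an age term with no age effect. The third column applies ANCOVA only if baseline PII differs at p < 0.05:

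| Case (baseline, ACT, WL SD) | t-test | ANCOVA always | ANCOVA if triggered |
|---|---|---|---|
| 1.0, 1.1, 1.0: power | 80.5% | 89.6% | 81.5% |
| 0.7, 1.4, 1.2: power | 80.1% | 79.8% | 80.0% |
| 1.2, 1.1, 0.8: power | 80.3% | 95.6% | 82.0% |
| 1.0, 1.1, 1.0: type I error | 5.0% | 4.9% | 4.4% |

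In the central case the trigger recovers about 1 of 9 points. With a baseline SD of 1.0 it needs a baseline difference of 1.99 × √(2/41) = 0.44 points to act. A separate 20,000-trial run gave a type I error of 7.3% if whichever of the two analyses was significant were reported. That is an extreme which the wording does not exclude.

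**The case against.** The natural reading is that the change-score t-test is primary. Section 6.1 sizes the trial on it and later refers back to the primary objective analysis as already described. The test is valid and adequately powered, so the choice is between two sound estimators. This is correct, and it is why the point concerns precision and prespecification, not error.

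The central case may flatter ANCOVA. Section 2.1.1 requires a PII mean of at least 2.0, or a score of 3 on three or more items, which allows a mean as low as 9/6 = 1.5. The pilot baseline mean was 2.1. If pilot scores were normal (an assumption), truncating at 2.0 or 1.5 gives a baseline SD of about 0.62 or 0.72. Over the same week-8 SDs the median gain is then +1.2 or +2.2 points, with ranges of 0 to +8.5 and 0 to +9.3. Retest variation between screening and baseline could widen the SD again. The objection to treating 9 points as the expected gain stands; no material loss appears in these cases either.

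The plan's trigger examples are gender and pain medication, so applying the trigger to baseline PII is a hypothetical. It shows only that the existing clause cannot stand in for planned adjustment.

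A late change also carries a credibility cost. Under section 5.3.1 the principal investigator reviews each patient's response data, participants know their arm (section 3.1.1), and section 7.5.2 indicates that some have finished. Simply confirming the t-test as primary would remove the ambiguity, but would leave the precision unused. The timing concern is real and has to be met by documenting when the change was made.

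**Conclusion.** The concern holds. Baseline PII is not a prespecified covariate, ANCOVA is discretionary and triggered by a significance test, and the form of the age stratification is missing. The t-test and the 41 per arm are sound for what they are.

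The gain from fixed adjustment is 80.5% to 89.9% power in the central case and about 0 to +15 points across the SDs examined; the lower part of that range is more likely if the entry cut-off narrows baseline scores. The documents cannot settle it. The trial's baseline SD, week-8 SDs and WL correlation are not given, and the pilot correlation of 0.24, from about 10 patients at 3 months, has a Fisher 95% CI of about −0.46 to 0.75. No gain is claimed for age. The gap in prespecification remains even if the gain is zero. The change should be made; confidence in its size is medium.

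**What to change.** State one primary analysis: ANCOVA of week-8 PII (or change) on randomised arm, with baseline PII and age stratum (16–24, 25–59) as prespecified covariates. Delete the baseline significance trigger. Keep the unadjusted t-test on change as a sensitivity analysis, and describe results within age strata as supportive.

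Use the same model, with each endpoint's own baseline value, for the baseline-to-8-week secondary comparisons only. It should not be carried to week 32: by then the WL arm has crossed over, and the study calendar gives it questionnaires at weeks 16 and 40, not 32.

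No extra patients, visits or data are needed. The cost is a dated, justified amendment before any between-arm analysis, with that timing recorded. If baseline PII added nothing beyond the change score, adjustment would cost about half a point of power or less (79.8% against 80.1% in the least favourable simulated case).

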Since previous studies have suggested that both in-person and internet-delivered ACT interventions are efficacious, the proposed study will implement an ACT intervention through two, 2-hour in-person sessions and online follow-up with adolescents and young adults with NF1 and PNs who experience chronic pain. We chose to use a slightly older age group than our pilot study; while the small number of patients in that study prohibited statistical analysis of different age groups, our clinical experience suggested that the younger adolescents had more difficulty understanding some of the concepts. A randomized study design is warranted based on previous literature supporting ACT's efficacy including our own preliminary data in patients with NF1, and because the two-group comparison design will allow us to establish whether patients improve more with ACT compared to patients doing their usual strategies to manage pain. Moreover, this design will allow for all participants to receive the intervention. The in-person plus internet format was chosen due to the infeasibility of conducting regularly-scheduled sessions with patients who live long distances from the NIH and because frequent out-of-home sessions are often unrealistic due to time or financial constraints. Finally, it should be mentioned that a notable proportion of individuals with NF1 have learning or attention deficits (Hyman et al., 2006). We do not expect this to pose a problem, since ACT and related therapies have demonstrated efficacy among individuals with developmental delays and attention problems (Robertson, 2011; Zylowska et al., 2008). While we will screen out prospective participants with significant cognitive deficits, we also made a number of modifications to the manual and workbook from our pilot study to make the intervention more appropriate for individuals with minor cognitive impairments, e.g., ADHD. For example, we eliminated exercises with more abstract metaphors and made several of the assignments more detailed and with more specific instructions. In addition, extending the intervention so that we maintain regular contact over 8 weeks hopefully will enable us to keep less focused individuals on track.

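### The pooled 'overall effect of ACT' in section 6.1 is an uncontrolled before-after change and should not be reported as a treatment effect

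*Combined protocol and SAP*

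**What the plan says.** The primary analysis in section 6.1 is the randomised comparison of PII change from baseline to week 8, ACT against wait list, "using a t-test with significance level of .05 (two-sided"). Section 1.2.3 explains what the control group is for: "the two-group comparison design will allow us to establish whether patients improve more with ACT compared to patients doing their usual strategies".

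Section 6.1 then adds a conditional secondary step, "comparing primary results from 0 to 8 weeks for ACT vs. 8 to 16 weeks for WL (receiving ACT starting at 8 weeks"). The condition is "if the results are similar (for example, $p>0.30$ approximately"). When it is met, "we will combine these groups to report the overall effect of ACT for 8 weeks". The same sentence goes on to "also examine changes from baseline to 8 weeks and 8 to 16 weeks using an appropriate statistical test".

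The section gives no comparator, time term or named test for the combined figure. It does not say that the wait-list arm's weeks 0-8, the only untreated period in the trial, enters it.

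**The concern.** Both periods in the pool are ACT periods. Their mean change estimates the effect of ACT plus any change that would have occurred without it, yet the plan calls the sum an effect of ACT. The question that section 1.2.3 sets, whether patients improve more than under usual management, is not the one this figure answers.

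Change without ACT is plausible. Entry requires a raised PII score (section 2.1.1.4), and the PII is also the primary outcome. It is a self-report over the past week (section 3.3.1.1) and is given repeatedly. The condition for pooling offers no protection against a trend common to both periods, because such a trend cancels in the comparison of one ACT period with the other.

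At stake is the reported size of the ACT effect. The pooled figure draws on up to 82 patients and has a smaller standard error than the randomised contrast. If it is read as a treatment effect, any non-specific improvement makes it too large. Its interval is also too narrow, since it omits the uncertainty in the control change.

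**Working it through.** **Inputs from section 6.1.** 41 patients per arm; SD of change 1.3 on ACT and 0.8 on wait list; difference to detect 0.68; two-sided 0.05; power 80%; pooling if p > 0.30.

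**Assumptions, because the plan is silent.** The pooled test is a paired (one-sample) t-test at two-sided 0.05 on all 82 patients. Change without ACT is 0.1, 0.2 or 0.3 PII points of improvement per 8 weeks. SD of change is 0.8 or 1.3, common to all periods. The wait-list arm's two changes have a within-patient correlation of -0.5 in the simulation.

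**The plan's own figure.** SD = sqrt((1.3² + 0.8²)/2) = 1.079. The normal approximation gives n = 2 × (1.960 + 0.842)² × 1.079² / 0.68² = 39.6, so 40 per arm. The exact t calculation gives power 79.5% at 40 and 80.5% at 41. The stated 41 is reproduced.

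**Bias.** With drift d in both periods, the pooled mean is off by d. With drift in weeks 0-8 only, it is off by (d + 0)/2 = d/2. Against the planned 0.68, a shared drift of 0.1, 0.2 or 0.3 is 15%, 29% or 44%.

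**Chance of pooling and then finding significance, with no true ACT effect.** For equal drift, the rate for the pooled test comes from the noncentral t with 81 df and noncentrality d × sqrt(82)/SD. Simulation shows that the condition passes in about 70% of trials whatever the shared drift, and that the pooled test's rate is practically the same among trials that pass. The rate over all trials is therefore about 0.70 times the rate given pooling, for example 0.70 × 0.609 = 0.43.

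| SD | Drift | Equal drift: given pooling | Equal drift: all trials | Drift in weeks 0-8 only: all trials |
|---|---|---|---|---|
| 0.8 | 0 | 5% | 3.5% | – |
| 0.8 | 0.1 | 20% | 14% | about 5% |
| 0.8 | 0.2 | 61% | 43% | about 9% |
| 0.8 | 0.3 | 92% | 64% | about 10% |
| 1.3 | 0 | 5% | 3.5% | – |
| 1.3 | 0.1 | 11% | 7% | about 4% |
| 1.3 | 0.2 | 28% | 20% | about 6% |
| 1.3 | 0.3 | 54% | 38% | about 8% |

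In the last column the condition does some work. At SD 0.8 the pass rate falls to 63%, 45% and 25% for drifts of 0.1, 0.2 and 0.3. In every scenario the randomised 0-8 week comparison rejects in about 5% of trials.

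**Standard errors**, taking SD 1.3 for both ACT periods and 0.8 for the untreated period:

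- Pooled before-after mean: 1.3/sqrt(82) = 0.144.
- Pooled mean minus the wait-list weeks 0-8 change: sqrt(1.69/82 + 0.64/41 - 2 × 0.5 × r × 1.3 × 0.8/41). This is 0.190 at r = 0, 0.206 at r = -0.25 and 0.221 at r = -0.5, where r is the correlation between the wait-list arm's two changes.
- Randomised contrast: sqrt((1.69 + 0.64)/41) = 0.238.

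**The case against.** The causal question is already answered by a controlled analysis. The pooled figure is a conditional secondary step, and the plan speaks of reporting it, without a named test or decision rule. All of this stands, so the rejection rates above illustrate an assumed test and do not describe one the plan specifies.

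The documents give no drift. Their one planning value is no change in the wait-list arm, and under it the pooled test behaves nominally. That stands too. But the wait-list arm's weeks 0-8 will measure this change, so it need not be assumed.

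Equal drift is the unfavourable case. Fluctuation after entry on a high score should fall mainly in weeks 0-8, where the condition for pooling partly detects it. The PII is also given at telephone screening (section 2.2.1), so some regression to the mean may precede baseline. This is why both drift patterns are shown. Repeat-testing effects or slower trends could persist into weeks 8-16.

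The clause on examining changes over 0-8 and 8-16 weeks might be read as setting the wait-list arm's untreated and treated periods side by side. The text does not say so and does not link that clause to the pooled figure.

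A reader might also infer that objective 1.1.2.1 makes the same mistake. It does not. It is worded as change within patients receiving ACT ("To examine baseline to 8-week changes in disease-specific quality of life, pain severity, pain-related anxiety, depression, and heart rate variability"), and objective 1.1.2.2 supplies the between-group contrast on the same outcomes.

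**Conclusion.** The point holds for the pooled analysis in section 6.1 and goes no further. As written, that analysis reports a before-after change under the name of a treatment effect, and its condition for pooling cannot detect a shared trend. This follows from which periods are pooled and needs no numerical assumption.

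The size does need assumptions: the drift, its pattern over the two periods, the SD, the paired t-test and full completion by 41 + 41 patients. Over all trials, the chance of a spurious pooled result runs from about 4% to 10% when drift is confined to weeks 0-8, and from 7% to 64% when it is equal in both, for drifts of 0.1 to 0.3. A reader might take 20%, 61% and 92% as rates over all trials. They apply only to trials that pass the condition, at SD 0.8 with equal drift.

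A reader might also infer that the trial's main conclusion is at risk. The documents do not support that: the primary comparison is randomised and keeps its 5% error at every drift examined. Nor do they say that the pooled figure will be the headline result.

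**What to change.** In section 6.1, replace the wording on the combined groups with text to this effect:

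- The effect of ACT is the randomised contrast in change from baseline to week 8.
- The mean change over the ACT periods of both arms is a descriptive within-group change and will not be called an effect of ACT.
- If a combined estimate is wanted, it is the mean change over both arms' ACT periods minus the wait-list arm's change over weeks 0-8, with a 95% confidence interval. It comes from a repeated-measures model with a within-patient covariance, because wait-list patients contribute to both terms. It assumes equal drift in the two 8-week periods, and the report will say so.

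That last assumption matters. If improvement without ACT of size d occurs only in weeks 0-8, the combined estimate subtracts d from a pooled drift of d/2 and so understates the benefit of ACT by d/2. It should therefore stay supplementary to the randomised contrast.

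The cost is SAP wording and, if the combined estimate is kept, one model on data already being collected. Its interval would be about 30-55% wider than the before-after interval (0.190/0.144 = 1.32 to 0.221/0.144 = 1.53). Objective 1.1.2.1 needs no change.
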